7.2 Study Duration

The total duration of the study for each participant will be a maximum of 17 weeks. Participants may receive study interventions for a maximum of 16 weeks, unless study

treatment is discontinued. Patients will be followed for up to one year following the last patient visit.

8.0 PRETREATMENT EVALUATION

8.1 Screening Period

The screening period consists of initial patient review, informed consent and GLTEQ. The GLTEQ is used to measure a person's current level of physical activity in terms of the duration and type of exercise. Ex-Onc research staff will maintain a screening log for all potential study participants. Each consented participant will be assigned a screening identification (Study ID) number in consecutive numerical order, beginning with 001.

Patients consented who do not subsequently meet eligibility criteria will be registered as ineligible. If research samples have been collected on those patients they will be discarded in accordance with regulations.

A new Study ID number will be assigned to a participant who is rescreened after originally failing to meet study eligibility.

8.2 Baseline Study Assessments

Participants will complete a symptom-limited CPET before undergoing all other baseline assessments. The baseline study assessment period will take place within 30 days of registration, except where otherwise noted.

Within 30 days of registration all participants will undergo the following baseline assessments:

1. Fasting research blood draw;
2. Fasting, non-invasive measurement of regional arterial stiffness (AS) and flow-mediated dilatation (FMD);
3. Resting assessment of left ventricular function using echocardiography;
4. Symptom-limited CPET with 12-lead ECG and pulmonary function testing;
5. Post-VO_{2peak} echocardiography;
6. Lifestyle questionnaire (**see Appendix A**); and
7. A dual-energy X-ray absorptiometry (DEXA) scan to assess body composition.

The completion of these assessments will take approximately 3 to 4 hours and will be conducted in the Ex-Onc Integrative Physiology Laboratories at Memorial Hospital (in Cardiology), the Rockefeller Outpatient Pavilion at 53rd Street (in Cardiology), or the Sidney Kimmel Center for Prostate and Urologic Cancers. Participants will be given an opportunity to eat a light snack following their fasted assessments. Participants will be encouraged to bring their own snack; however, the Ex-Onc team will also have extra snacks, such as granola bars, available in case participants do not bring their own.

At the baseline visit, participants will also receive a welcome packet (**Appendices C, D, F**), which contains information about the program and an easy-to-use study calendar.

The DEXA scan will be performed at either the BAIC or the Rockefeller Outpatient Pavilion.

To maximize internal validity, we will try to schedule study endpoint assessments in the same order as they were completed at baseline, midpoint and followup.

All baseline study assessments are described in **Table 1**.

Table 1. Baseline Study Assessments

REQUIRED ASSESMENT	DESCRIPTION
Resting left ventricular function by 3-dimensional echocardiography (3DE)	
Three-dimensional transthoracic echocardiograms will be performed by experienced sonographers and acquired with commercially available equipment (Vivid 7 or E9, GE Healthcare, Milwaukee, WI).
 
Following completion of the 2DE, a full volume dataset will be acquired using a matrix array transducer with gated 4 beat acquisitions for assessments of left ventricular (LV) volumes by 3DE. A 3DE acquisition of the entire LV will be generally performed in <10 seconds. All assessments will be stored digitally for offline analyses performed using EchoPAC PC workstation (version BT11, GE Medical, Milwaukee, WI).
 
Conventional 2D measurements of LV dimensions, Doppler, and diastolic function parameters will be performed and averaged over 3 cardiac cycles according to American Society of Echocardiography guidelines.²⁹⁻³¹
 
Left ventricular volumes and left ventricular ejection fraction (LVEF) by 3DE will be determined by manipulating the full volume dataset to derive conventional apical 4-, 3-, and 2-chamber views using TomTec offline analysis software (4D LV-Function, Unterschleisheim, Germany). After selection of reference points, a 3D endocardial contour will be automatically generated and manual adjustment will be performed as necessary. The resultant end-diastolic (EDV) and end-systolic volumes (ESV) will be used to calculate LVEF.³²

Symptom-limited CPET to assess peak oxygen consumption (VO_{2peak})	
VO_{2peak} will be evaluated using an electronic motorized treadmill test with 12-lead ECG monitoring (Mac® 5000, GE Healthcare) performed by certified exercise physiologists.
 
CPET provides assessment of peak oxygen consumption (VO_{2peak}). Expired gases will be analyzed continuously by a metabolic measurement system (Parvo Medics TrueOne 2400).
 
During the test, participants will begin walking on a treadmill at a participant-specific designated speed and grade for approximately 2 minutes. The speed and/or grade will then be increased every 1–2 minutes until exhaustion or a symptom-limitation is reached.
 
During exercise, oxyhemoglobin saturation will be monitored using finger pulse oximetry, while blood pressure will be measured manually by auscultatory sphygmomanometer every two minutes (± 1 minute).

	The CPET may be terminated at the discretion of the exercise physiologist if abnormal ECG findings or abnormal response to exercise is observed, or if acceptable test criteria are not met.
Post VO_{2peak} left ventricular function by 2-dimensional echocardiography (2DE)	As soon as possible following completion of the CPET, participants will be placed in the supine position and 2DE grayscale images will be obtained in the apical 4-, 3-, and 2-chamber views. Wall motion scoring index (WMSI) will be calculated at rest and post-exercise using the 17 segment model by adding the individual segment scores (1 = normal; 2 = hypokinesia; 3 = akinesia; 4 = dyskinesia) and dividing by number of segments scored. ²⁹ 2D LV volumes and LVEF will be calculated offline using the modified Simpson's biplane method. Cardiac output will be calculated as the product of LV stroke volume and heart rate, indexed to body surface area (BSA).
Pulmonary function testing	Pulmonary function will be determined using standard spirometry. All measures will be performed in a sitting position according to the American Thoracic Society guidelines. ³⁶
Regional arterial stiffness	
Conduit regional artery stiffness of the entire aorta will be assessed non-invasively by measuring carotid-femoral pulse wave velocity (PWV) using 2 hand-held tonometers (SPT-301 Millar Instruments, Houston, TX).
 
Carotid and femoral artery waveforms will be recorded simultaneously with the mechanotransducers directly applied to the skin over the greatest area of pulsation. Twenty consecutive reproducible beats will be collected simultaneously at both sites, with a concurrent electrocardiograph to obtain R-R intervals.
 
Pulse transit time will be determined as the difference in time from R interval to systolic upstroke at each location. Systolic upstroke will be determined by identifying the foot or —notch of the blood pressure waveform. This will be done by applying a band pass filter between 5-30 Hz, selecting the minimum value of the filtered signal.
 
Pulse distance will be determined using anthropometric measuring tape subtracting the distance from carotid measurement to sternal notch from the distance from sternal notch to femoral pulse measurement. This method has been shown to be the optimal non-invasive measurement compared to invasive measure. PWV will then be determined by taking the pulse transit time/distance.

Flow-mediated dilatation (FMD) to assess endothelial function	
Peripheral artery flow-mediated dilatation (FMD) will be performed on one arm with the subject in a supine position with the forearm extended and slightly supinated.
 
A rapid inflator blood pressure cuff will be placed on the forearm just distal to the antecubital crease and the brachial artery will be imaged using high-resolution B-mode ultrasound and a 7.5MHz linear array transducer (Terason, t3200). Ten-second r-wave triggered digital clips (artery diastole) will be captured at baseline (following 10min of supine rest), during five minutes of forearm occlusion, and a 120 sec r-wave triggered digital clip will

	
be captured beginning at cuff deflation (hyperemia) as previously described.³⁷
 
Offline analysis using specialized software (Brachial Tools, Medical Imaging Applications, Illinois) will permit for identification of peak dilation and dilation at specific pre-specified time points (60, 120 sec).³⁷

Dual energy x-ray absorptiometry (DEXA) to assess body composition	
Body fat percentage, and lean and fat body mass will be assessed by dual energy x-ray absorptiometry using a Lunar Prodigy multiple detector fan-beam densitometer (GE Medical Systems, Madison, WI). After calibration with an anthropomorphic phantom, single-beam, whole-body scanning will be employed on supine-positioned subjects. Data will be obtained from each scan for fat and lean body mass expressed to the nearest tenth of a gram (and percent) for the total body region, as well as in defined body zones (e.g., legs, trunk and arms).
 
In the two hours prior to the DEXA scan, participants will be asked to avoid a large meal, avoid caffeine, avoid alcohol, and avoid tobacco. Participants will also be instructed to avoid strenuous activity for at least twelve hours before the scan.
 
Efforts will be made for baseline and follow up DEXA assessments to be performed on the same machine.

Patient-reported outcomes (via Lifestyle Questionnaire, Appendix A)	
Patient-reported outcomes will be assessed using a patient-administered questionnaire to assess quality of life, fatigue, pain, and sleep quality.
 
 • Quality of Life (QOL) will be assessed by the Functional Assessment of Cancer Therapy–Breast (FACT-B) scale developed for the assessment of patient symptoms and QOL in breast cancer patients.³⁸ • Fatigue will be assessed using the 13-item FACIT-Fatigue scale for the assessment of fatigue in cancer patients.³⁹ • Pain will be assessed using the 10-item Brief Pain Inventory (BPI) which was designed to measure multiple clinically relevant aspects of pain such as pain intensity and interference from pain in cancer populations.⁴⁰ • Sleep Quality will be assessed by the Pittsburgh Sleep Quality Index (PSQI).⁴¹ • Medical Outcomes Trust Short Form Health Survey (SF-36): The SF-36 is a psychometrically robust self-report questionnaire that measures general health-related quality of life in 8 domains of health: physical functioning (SF-36 PF), role limitations caused by physical health (role-physical), bodily pain, general health perceptions, vitality, social functioning, role limitation due to emotional problems (role-emotional) and mental

	health. ⁴²
Complete Blood Count (CBC), Glucose and Lipid Panel	Blood will be drawn per clinical practice and analyzed by MSK Clinical Chemistry.
Fasting research blood draw	Blood collection should take place prior to the initiation of any-study related interventions, whenever possible.

Following the completion of all baseline assessments and final confirmation of eligibility, participants will be randomized to one of the three study arms.

Participants who do not meet eligibility criteria will be informed of their status and considered a screen failure.

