2.2 Secondary Objectives

- To compare the effects on resting and exercise cardiac function;
- To compare the effects on pulmonary function;
- To compare the effects on arterial stiffness;
- To compare the effects on endothelial function;
- To compare the effects on body composition;
- To compare the effects on patient-reported outcomes (e.g., quality of life, fatigue) ;
- To collect and bank blood samples for future correlative studies; and
- To assess and compare the safety of supervised aerobic training.

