12.2 Secondary Study End Points

- Resting left ventricular function by 3-dimensional echocardiography (3DE): Three-dimensional transthoracic echocardiograms will be performed by experienced sonographers and acquired as outlined in Section 8, Table 1.

- *Pulmonary Function* will be determined using standard spirometry. All measures will be performed in a sitting position according to the American Thoracic Society guidelines.³⁶
- *Post-exercise VO_{2peak}* : Post-exercise VO_{2peak} and left ventricular ejection fraction (LVEF) will be assessed via 2-D echocardiography. Images will be obtained as described in Section 8, Table 1.
- *Regional Arterial Stiffness*: Assessment of arterial stiffness will be completed as described in Section 8, Table 1.
- *Flow-mediated dilatation (FMD)*: Endothelial function will be evaluated by peripheral artery flow-mediated dilatation. FMD will be performed on the left arm, as described in Section 8, Table 1.
- *Body Composition*: Body composition, including body fat percentage, fat mass, and lean body mass, will be assessed by DEXA using the methods described in Section 8, Table 1.
- *Patient-Reported Outcomes*: Patient-reported outcomes will be assessed using a patient-administered Lifestyle Questionnaire (see **Appendix A**) to assess quality of life, fatigue, pain, and sleep quality.
 - *Quality of Life (QOL)* will be assessed by the Functional Assessment of Cancer Therapy–Breast (FACT-B) (version 4) scale. The FACT-B contains 37-items, divided into four primary subscales for physical well-being (7 items), functional well-being (7 items), emotional well-being (6 items), and social/family well-being (7 items) that comprise the FACT–General (FACT-G) scale, in addition to a breast cancer subscale (10 items). The five subscales will be summed to obtain the FACT-B score (for a total score of 148).³⁸ We will also compute the FACT-G score (27 items, excluding the breast cancer subscale; total score of 108). All items are rated on a 0 to 4 Likert scale, using the following response format: 0 = not at all; 1 = a little bit; 2 = somewhat; 3 = quite a bit; 4 = very much. Respondents are asked to respond to each question as it applies to the past 7 days. Higher scores on the FACT-B indicate higher QOL. Internal consistency for the FACT-G and FACT-B is well established.

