14.3 Primary and Secondary End Point Analyses

14.3.1 Primary End Point Analysis: The primary objective will be to compare the effects of supervised linear aerobic training (Arm A) versus supervised nonlinear aerobic training (Arm B), relative to progressive stretching (attention-control group) (Arm C), on VO_{2peak} in women with operable breast cancer following the completion of primary adjuvant therapy.

An intent-to-treat statistical analysis will be conducted. Baseline characteristics will be compared using the Fisher exact test for categorical variables or a Wilcoxon rank sum test for continuous variables. The primary end point comparison will be analyzed using a multiple regression model to test for differences among and between the study arms in VO_{2peak} from baseline to the follow-up assessment (Week 17). The regression model will include the stratification factors [i.e., treatment with chemotherapy (yes vs. no) and current treatment with endocrine therapy (yes vs. no)].

In the absence of evidence to the contrary, multiple imputation strategies for missing Week 17 VO_{2peak} data will be performed assuming data were missing at random using logistic regression. Results will be aggregated over 20 imputed sets using the variance formula by Rubin. In addition, a per-protocol analysis will be performed using a multiple regression model to test for differences among and between the study arms in VO_{2peak} from baseline to the follow-up assessment (Week 17) on the basis of exercise adherence to the supervised aerobic training sessions (<80% versus ≥80%). In the event that groups are unbalanced on medical or demographic characteristics at baseline, we will also perform a sensitivity analysis that includes these factors in the model.

14.3.2 Secondary End Point Analyses: As for the primary end point, the intention-to-treat principle will be employed for analysis of all secondary end points. Multiple regression models will be used to test for differences among and between the study arms in secondary end points from baseline to the follow-up assessment (Week 17). The regression model will include the baseline value of the end point, as well as any other baseline characteristics that are not balanced between groups. All secondary end points are continuous.

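### Table 1 defines pulse wave velocity as transit time over distance, the reciprocal of a velocity, and no other section corrects it

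*Combined protocol and SAP*

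**What the plan says.** Section 2.2 lists arterial stiffness among the secondary objectives: "To compare the effects on arterial stiffness". Table 1 in Section 8.2, under regional arterial stiffness, says it is assessed by "measuring carotid-femoral pulse wave velocity (PWV) using 2 hand-held tonometers". The same cell then defines two inputs and a rule:

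- Transit time: "Pulse transit time will be determined as the difference in time from R interval to systolic upstroke at each location".
- Pulse distance, taken with a measuring tape: "subtracting the distance from carotid measurement to sternal notch from the distance from sternal notch to femoral pulse measurement".
- Derivation: "PWV will then be determined by taking the pulse transit time/distance".

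Section 12.2 gives no formula of its own: "Assessment of arterial stiffness will be completed as described in Section 8, Table 1". For the analysis, Section 14.3.2 says: "Multiple regression models will be used to test for differences among and between the study arms in secondary end points". The model includes the baseline value, and all secondary end points are treated as continuous.

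**The concern.** The rule inverts the quantity it claims to produce. A velocity is a length divided by a time, and the rule divides a time by a length. Because Section 12.2 defines the end point only by pointing to Table 1, the inverted rule is the sole definition of this end point.

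PWV serves as a stiffness measure because the pulse travels faster in a stiffer artery. If transit time over distance were computed and the result labelled PWV, stiffer arteries would get lower values. A reduction in stiffness from training would then appear as an increase in PWV. Section 12.2 says that higher is better for FACT-B, FACIT-Fatigue and physical functioning. It gives no such statement for PWV that could alert an analyst to the reversal.

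**Working it through.** The documents give no PWV value, SD, effect size or power, so there is no stated figure to reproduce. The check is dimensional, followed by an illustration. The distances and times below are assumptions, not trial data.

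**1. Units.** Let t be transit time (s) and D pulse distance (m), both as defined in Table 1.
- Velocity: D/t, in m/s.
- Rule as written: t/D, in s/m, which equals 1/(D/t).

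**2. Ordering.** At three assumed distances and three assumed transit times:

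| D (m) | t (s) | D/t (m/s) | t/D (s/m) |
|---|---|---|---|
| 0.4 | 0.050 | 8.0 | 0.125 |
| 0.4 | 0.0625 | 6.4 | 0.156 |
| 0.4 | 0.080 | 5.0 | 0.200 |
| 0.5 | 0.050 | 10.0 | 0.100 |
| 0.5 | 0.0625 | 8.0 | 0.125 |
| 0.5 | 0.080 | 6.25 | 0.160 |
| 0.6 | 0.050 | 12.0 | 0.083 |
| 0.6 | 0.0625 | 9.6 | 0.104 |
| 0.6 | 0.080 | 7.5 | 0.133 |

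At each distance the fastest wave gets the lowest value under the written rule. The reversal does not depend on the assumed distance.

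**3. A change within one participant.** Take D = 0.50 m and t = 60 ms.
- Before: 0.50/0.060 = 8.33 m/s; as written, 0.060/0.50 = 0.120 s/m.
- After PWV falls to 7.5 m/s: t = 0.50/7.5 = 0.0667 s; as written, 0.0667/0.50 = 0.133 s/m.
- Change in velocity: 7.5/8.33 = 0.90, a 10% fall. Change as written: 0.133/0.120 = 1.11, an 11% rise.

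**4. Why summaries cannot simply be re-signed.** Use the D = 0.5 m rows.
- A fall from 10.0 to 8.0 m/s is 2.0 m/s, or 0.125 − 0.100 = 0.025 s/m.
- A fall from 8.0 to 6.25 m/s is 1.75 m/s, or 0.160 − 0.125 = 0.035 s/m.

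The larger change on one scale is the smaller on the other. Means behave the same way. The mean of 10.0 and 6.25 m/s is 8.125 m/s. The mean of 0.100 and 0.160 s/m is 0.130 s/m, and its reciprocal is 1/0.130 = 7.69 m/s. Section 14.3.2 mentions no log transformation, so the planned regressions on the two scales would give different estimates and p-values, not mirror images.

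**5. What can be recovered.** For a single participant, 1/(t/D) = D/t exactly. The exception is a stored value that averages a ratio computed beat by beat. Table 1 collects twenty beats but does not say at which step they are averaged.

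**6. Scale.** In step 3 the two numbers differ by a factor of 8.33/0.120, about 70.

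**The case against.** The strongest reply is that this is a drafting slip with no practical effect. The same cell names a velocity and correctly defines a time and a length, so a competent operator has all that is needed to form distance over time. The slash might even be shorthand for deriving PWV from both quantities, although a quotient is the more natural reading. If it is shorthand, the protocol has no PWV formula at all and the line still needs correcting.

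Misreading the result also takes two errors in a row: applying the rule literally, and then treating the output as a velocity. Values of about 0.12 where about 8 is expected should stand out, and the Quality Assurance section provides for routine reports on inconsistencies. Even if the error got through, participant-level values could be inverted and the model rerun, with no one re-measured.

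Much of this stands, and it limits the consequence. It does not rescue the text, which is the only definition of the end point and is wrong as written.

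A reader might infer that the arterial stiffness result will be reported in the wrong direction, or that data already collected are compromised. The documents support neither. They show no PWV derivation code, no units and no stored value. Nor do they say how many participants have PWV data. At DUMC 115 were randomized, and the number completing study procedures is given as 109 in Section 1.0 and 106 in Section 16.3.

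**Conclusion.** The point holds as an error in an end point definition, of moderate severity. The written rule is the reciprocal of the named quantity, and nothing elsewhere in the protocol or SAP corrects it. The reversed direction is conditional on the rule being applied literally and the output being read as a velocity. In that case group means and coefficients would have to be recomputed from participant-level values.

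The scope is one secondary end point with no stated effect size or power. VO2peak, the eligibility criteria and the sample size do not use PWV.

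Two assumptions carry the argument. The illustrative distances and times are assumed, though the reversal does not depend on them. That a faster wave means a stiffer artery is the premise for using PWV here, and the documents do not spell it out. The 10% and 11% figures describe PWV and its reciprocal; the documents give no scale that converts them to a percentage change in stiffness.

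**What to change.** In Table 1, replace the derivation sentence with: PWV (m/s) = pulse distance / pulse transit time; higher values indicate greater stiffness. Add the step at which the twenty beats are averaged, so that the rule is complete.

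Before pooling, confirm from the derivation code or from the recorded times and distances that all stored PWV values from DUMC and MSK participants follow this formula, and invert any that do not. Check each site against its source inputs and not only against the other site. A comparison between sites would show a mismatch, but not an error common to both, and MSK data-entry staff cannot see DUMC records (Section 16.5).

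The cost is a short text correction and a code check. No new measurements are needed.
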